8.1. Screening and Study Schedule

The screening visit is scheduled -60 to -9 days before the first vaccination. Fully informed, written consent must be obtained from each subject prior to conducting any study procedure. Two consent forms will be signed; a consent form for study participation and a separate consent form for HIV testing. To assess understanding, a comprehension assessment will be administered after the subjects sign the study participation written consent. The following evaluations/procedures will be carried out:

- Oral and/or video presentation of clinical trial design, risks and study schedule
- Review of informed consent document
- One-on-one discussions with principal investigator or subinvestigator
- Signature of informed consent document (see section 9.2 for informed consent process)
- Comprehension test (minimum of 70% accuracy required for participation, two attempts allowed)
- Medical history – between Days -60 to -9
- Physical examination – between Days -60 to -9
- Vital Signs – between Days -60 to -9
- Screening laboratory analysis (allowable time period for accepting test):
 - Complete blood count (between Days -60 to -9)
 - Serum transaminases (ALT/AST) (between Days -60 to -9)
 - Na, K+, CL-, HCO₃, glucose, BUN and creatinine (between Days -60 to -9)
 - Total serum IgA (between Days -60 to -9)
 - Pregnancy test (urine -hCG) for women, as well as 0-24 hours before each vaccination
 - HLA-B27 (between Days -60 to -9)
 - Serology screening (Anti LPS Antibody) for prior *Shigella* exposure (between days -60 to -9)
 - Serum HIV 1/2 antibody (between days -14 to -2)
 - Hepatitis B surface antigen (HBsAg) (between days -14 to -2)
 - Hepatitis C virus Ab (between days -14 to -2)

Additionally, approximately 7 days prior to vaccination (allowable range: Days -14 to -2), subjects will have a follow-up medical history and brief physical exam to ensure ongoing eligibility. If the initial screening is within the -14-day window, it can count as both the initial screening and pre-vaccination visit (and all screening activities will be conducted at the one visit). Blood, saliva, and stool will be collected for baseline serology testing. Additional

instruction will be reviewed with each subject to include review of the study visit schedule, preparation procedures for saliva collection, and procedures for stool collection and storage. The following screening laboratory analyses will be carried out (below tests will not be repeated if the initial screening visit occurs during the day -14 to -9 window):

- Repeat complete blood count
- Repeat serum transaminases (ALT/AST)
- Repeat Na, K+, Cl-, HCO₃, glucose, BUN and creatinine
- Serum HIV 1/2 antibody (between Days -14 to -2)
- Hepatitis B surface antigen (HBsAG) (between Days -14 to -2)
- Hepatitis C virus (anti-HCV antibody) (between Days -14 to -2)

A screening test for any of the above assessments may be repeated in the event of a laboratory error (i.e., hemolyzed sample) or in the event the screening physician believes: 1) the laboratory test has identified a normal variant of a healthy state (i.e., below normal hemoglobin in a menstruating female, or cyclic reductions in absolute neutrophil count in subjects of African descent) and 2) the variant is no more than a Grade 1 abnormality. This repeat screening applies to the initial screening tests [(executed between -60 to -9 days) and the repeat screening labs if executed (between days -14 to -2)]. If a repeat screening blood test is performed, only the results of the second test will be used to determine eligibility.

The WRAIR Clinical Trials Center (CTC) may use a screening protocol in recruiting volunteers for this study. All screening procedures outlined in this section may be completed under this screening protocol.

During this screening process, the laboratory assays will be reviewed to determine if any clinical laboratory abnormalities exist that would preclude study participation. Subjects who have only 1 mild (grade 1) abnormality may be included if the PI determines that their participation will not present undue risk to the subject. Subjects with 2 or more mild abnormalities may be included in the study only with the consensus of the PI and the research monitor. Subjects with clinical laboratory abnormalities of greater than mild severity will not participate in this clinical trial. The clinical toxicity grading scale that will be used as a guideline is based on the scale used by the Division of AIDS (DAIDS) for adverse events and the guidance from the US Food and Drug Administration (FDA) Center for Biologics Evaluation and Research. If any additional safety labs are performed, either scale may be utilized.

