- One or more SAEs, including grade 4 adverse events or laboratory abnormalities.
- Two or more grade 3 adverse events or laboratory abnormalities of the same type.
- One or more grade 3 laboratory abnormalities.
- Two or more grade 2 laboratory abnormalities.

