11.4.1. Protocol Safety Review Team

The Protocol Safety Review Team (PSRT), comprised of the Principal Investigator, the PATH Medical Officer, and the Independent Research Monitor will routinely monitor safety throughout the duration of the trial. The PSRT will be chaired by the Independent Research Monitor, and may seek additional independent expert medical opinion as dictated by needs. Emmes will prepare blinded safety reports for review by the PSRT. These reports will provide at a minimum the following information: 1) accrual and participant status data with regard to completion of study vaccinations and study visits; and 2) summaries of solicited and unsolicited adverse events including safety labs. The PSRT safety review will be conducted electronically (or by teleconference when needed). In addition to safety review, the PSRT may elect to discuss trial conduct issues that impact study integrity and participant safety. These may include but are not limited to data quality, critical monitoring findings, study product, research specimens, etc.

Emmes will also notify the PSRT of ad hoc safety reviews whenever it is aware of SUSAR or adverse events that meet pre-specified study pause criteria as per section 8.10.

In addition to routine review of safety information, a central role of the PSRT is the blinded review of safety data for the recommendation of whether to progress to the next dose level in each cohort and to the next cohort. Cumulative safety data will be available continuously for review by PSRT members, and safety reports will be prepared for each PSRT deliberation of dose escalation and progression to subsequent cohorts.

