3.3. Study Definitions and Derived Variables

3.3.1. Adverse Event (AE)

An AE, as defined by the ICH guideline for GCP, is “Adverse event means any untoward medical occurrence associated with the use of a drug in humans, whether or not considered drug related.”

An AE is considered any adverse change or exacerbation from a baseline condition that occurs following the initial administration of an investigational product whether or not the event is considered to be related to the investigational product. Examples of this include but are not limited to the following:

- Adverse changes including new signs and symptoms, intercurrent illness modifying the clinical course, or the worsening of a baseline condition including the increased frequency of an event or an increased intensity of a condition
- Concomitant disease with onset or increased severity after the start of study product administration
- A new pattern in a preexisting condition occurring after the receipt of investigational product that may signal a clinically meaningful change
- Clinically significant changes in laboratory values

This definition includes exacerbations of pre-existing conditions. Stable pre-existing conditions which do not change in nature or severity during the study are not considered AEs; however, these should be reported as part of the medical history. However, if this condition deteriorates (e.g., increases in frequency or severity grade) during the study, it should be recorded as an AE.

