6.6. Protocol Safety Review Team (PSRT)

No formal interim analyses involving hypothesis testing were planned. The analyses described here are for safety review only, by the PSRT.

A PSRT will be established by PATH to monitor the study and to provide independent, non-binding advice on safety and ethics. The PSRT will be composed of the Principal Investigator, the PATH Medical Officer and the Independent Research Monitor who will periodically review the conduct and safety of the study. The PSRT will be supported by an unblinded secretary and an unblinded biostatistician, both from Emmes. The responsibilities and procedures of the PSRT are defined in the PSRT Charter.

Three blinded reviews of data will be conducted by the PSRT when safety, reactogenicity and clinical lab data from all subjects in a cohort are available up to 7 days post-dose 3 of the study vaccine. Each report will be provided to the PSRT for their review to determine whether the study can continue to enroll for the next, dose-escalating cohort or whether the study should be stopped. At the time of each interim analysis, PATH will neither have access to the individual treatment assignments, nor to any unblinded safety reports (if applicable), but will be provided with aggregated safety results per cohort to allow strategic decisions for the future of the study.

The following summaries will be generated by group and all analyses will be performed on the safety population. Each PSRT report will be based on a unique frozen data base.

1. Occurrence of solicited local AEs during a 7-day follow-up period (i.e., on the day of vaccination and 7 subsequent days) after the first, second and third dose.
2. Occurrence of solicited systemic AEs during a 7-day follow-up period (i.e., on the day of vaccination and 7 subsequent days) after the first, second and third dose.
3. Occurrence of unsolicited AEs after each dose and up to 28 days after the third dose (dose intervals are 21 days).
4. Occurrence of hematological (red blood cell, white blood cell, differentials, hematocrit, platelet count and hemoglobin) and biochemical (Sodium, Potassium, Glucose, AST, ALT, BUN and Creatinine) laboratory abnormalities within 7 days of each dose.
5. Occurrence of SAEs at any time during the study at the time of data freeze.

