	Range				
Pre-Vaccination 1	N				
	Mean (SD)				
	Median				
	Range				
Day 7 Post-Vaccination 1	N				
	Mean (SD)				
	Median				
	Range				
	Mean change from baseline (SD)				
	Median change from baseline				
Day 7 Post-Vaccination 2	N				
	Mean (SD)				
	Median				
	Range				
	Mean change from baseline (SD)				
	Median change from baseline				
Day 7 Post-Vaccination 3	N				
	Mean (SD)				
	Median				
	Range				
	Mean change from baseline (SD)				
	Median change from baseline				
Final “on therapy” value	N				
	Mean (SD)				
	Median				
	Range				
	Mean change from baseline (SD)				
	Median change from baseline				

Baseline values are from pre-vaccination 1. If missing, then screening values will be used.

Table will also include:

Hematology

WBC Count ($10^6/\mu\text{L}$)*	RBC Count ($10^3/\mu\text{L}$)**	Hemoglobin (g/dL)*
Hematocrit (%)*	Platelet count ($10^3/\mu\text{L}$)	Absolute Neutrophils (cells/ μL)
Absolute Lymphocytes (cells/ μL)	Absolute Monocytes (cells/ μL)	Absolute Eosinophils (cells/ μL)
Absolute Basophils (cells/ μL)		

Chemistry

Sodium (mmol/L)	Potassium (mmol/L)*	Chloride (mmol/L)
BUN (mg/dL)	Creatinine (mg/dL)**	Bicarbonate (mmol/L)
Glucose (mg/dL)	AST (U/L)	ALT (U/L)

[Programming note: * reported to one decimal place, ** 2 decimal places. All others are integers].

Table 32: Final On Therapy Hematology and Serum Chemistry Severity Grading, by Treatment Group and Relationship¹ to IP - Safety Population

		InvaplexAR 2.5 μg (N=X)	InvaplexAR 10 μg (N=X)	InvaplexAR 25 μg (N=X)	Placebo (N=X)
		n (%)	n (%)	n (%)	n (%)
WBC					
All values	Normal				
	Abnormal ²				
	Mild				
	Moderate				
	Severe				
	Potentially Life-Threatening				
Not Related to IP	Mild				
	Moderate				
	Severe				
Related to IP	Mild				
	Moderate				
	Severe				
[other parameters]					

N=Number of subjects in the safety population.

¹ Relationship is assessed only for mild or greater values reported as adverse events.

² Outside the normal range but less than mild.

[See above for complete list of parameters]

A.3.3 Vital Signs

Table 33: Vital Signs: Descriptive Statistics by Visit and Treatment Group - Safety Population

	Pulse Rate (beats/min)				Systolic Blood Pressure (mm Hg)				Diastolic Blood Pressure (mm Hg)			
	Inva plexar-DETOX				Inva plexar-DETOX				Inva plexar-DETOX			
	2.5 µg (N=X)	10 µg (N=X)	25 µg (N=X)	Placebo (N=X)	2.5 µg (N=X)	10 µg (N=X)	25 µg (N=X)	Placebo (N=X)	2.5 µg (N=X)	10 µg (N=X)	25 µg (N=X)	Placebo (N=X)
Baseline¹												

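### SAP Table 32 shows final laboratory grades without the baseline grade, so a Grade 1 value present at entry and unchanged counts as a post-vaccination Mild value

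*Protocol*

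**What the plan says.** **Entry.** Protocol 8.1 states that "Subjects who have only 1 mild (grade 1) abnormality may be included" if the PI sees no undue risk, and that "Subjects with 2 or more mild abnormalities may be included in the study only with the consensus of the PI and the research monitor". The ceiling is explicit: "Subjects with clinical laboratory abnormalities of greater than mild severity will not participate in this clinical trial".

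**Grading.** Protocol Tables 10 and 11 (SAP Tables 5 and 6) grade by fixed cut-offs. Only hemoglobin has a rule that looks at the subject's own baseline: its footnote requires a fall of at least 0.5 g/dL before an AE is recorded.

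**Displays.** SAP 8.6 plans descriptive statistics with change from baseline (Table 31) and a separate severity summary (Table 32). Table 32 grades the final on-therapy value in three sets of rows: all values, not related and related. Its first footnote says "Relationship is assessed only for mild or greater values reported as adverse events". There is no baseline row or column.

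**AE definition.** SAP 3.3.1 says "Stable pre-existing conditions which do not change in nature or severity during the study are not considered AEs". The laboratory endpoint in SAP 3.2.1 is the occurrence of laboratory-based AEs.

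**PSRT report.** SAP 6.6 item 4 lists the occurrence of hematological and biochemical "laboratory abnormalities within 7 days of each dose". Protocol 11.4.1 describes the reports as including "summaries of solicited and unsolicited adverse events including safety labs".

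**The concern.** Table 32 is the only planned summary of laboratory grade by treatment group for all values, whether or not they were reported as AEs. Protocol 12.1.1 places safety laboratory measures in the primary analysis. A subject who enters with a Grade 1 neutrophil count and still has it at the last draw appears in the Mild row, exactly like a subject whose count fell after vaccination. The table cannot tell the two apart.

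This matters more here than in a trial randomized across doses. The three dose cohorts are enrolled one after another, and randomization is only between vaccine and placebo within a cohort. Admission with a Grade 1 value is discretionary, so its frequency can differ between cohorts for reasons unrelated to dose. SAP 6.1 nevertheless puts the dose groups in adjacent columns with placebo pooled at the end. A difference in entry status could then be read as a dose difference in Mild values.

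**Working it through.** **1. The plan's own precision figure.** For 0 events in 16, the exact two-sided 95% upper limit is 1 − 0.025^(1/16) = 0.206. This reproduces the 0–21% in Protocol 12.2 and SAP 5, which is not in dispute.

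**2. Which rows can contain an unchanged entry value?**

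| Count | Relative to baseline? | Can hold an unchanged Grade 1 entry value? |
|---|---|---|
| Laboratory AEs (SAP 3.2.1 with 3.3.1) | Yes | No |
| Table 32, related and not-related rows | Yes, limited to reported AEs | No |
| Table 32, All values, Mild | No | Yes |
| Table 32, All values, Moderate and above | No, but entry above Grade 1 is excluded | No |
| SAP 6.6 item 4 | Not stated | Depends on the reading |
| Protocol 8.10 laboratory counts | Start at Grade 2 and require relatedness | No |

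**3. Weight of one subject.** One subject is 1/16 = 6.25 points of that test's Mild rate in a dose group, and 1/12 = 8.3 points in pooled placebo (3 × 4 = 12). As an illustration, 2/16 Mild (12.5%, exact 95% CI 1.6–38.3%) becomes 0/16 (0–20.6%) if both values were present at entry and unchanged.

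**4. How many subjects?** The documents do not say. Assume that a proportion p of enrolled subjects has at least one Grade 1 value at entry, on any test, that lasts to the final draw. The expected number in a group of 16 is 16p, and the chance of at least one is 1 − (1 − p)^16.

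| p (assumed) | Expected of 16 | Chance of at least one |
|---|---|---|
| 5% | 0.8 | 56% |
| 10% | 1.6 | 82% |
| 20% | 3.2 | 97% |
| 30% | 4.8 | over 99% |

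If only half of such values persist, the 5% and 30% rows fall to 0.4 (33%) and 2.4 (93%).

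**5. Per test.** Step 4 counts any test, whereas Table 32 is read test by test. Thirteen analytes are graded (six hematology, seven chemistry). Spread evenly, for illustration only, 1.6 to 4.8 subjects become 1.6/13 = 0.12 to 4.8/13 = 0.37 per test per group, or 0.8 to 2.3 points. Clustering in one test would give more for that test and less for the others.

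**The case against.** The strongest reply is that baseline is already used where it counts. The laboratory endpoint is an AE endpoint, and an unchanged condition is not an AE. The AE tables that carry p-values rest on that definition, while Table 32 has no p-value. Table 31 gives mean and median change from baseline. Listings 11 and 12 give each subject's Screening and Day -7 values with severity, so in a trial of 60 the entry grade can be recovered. The average per-test effect is small beside a 0–21% interval. All of this stands, and it limits the point to one set of rows. It does not remove it: mean change does not show how many subjects changed grade, and a listing is not a summary by group.

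A reader might also infer three stronger things that the documents do not support.

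- *That the PSRT will receive counts mixing entry status with vaccine effect.* SAP 6.6 item 4 speaks of abnormalities, but Protocol 11.4.1 describes AE summaries, and no PSRT table shell is given. This is an ambiguity, not a shown error. The PI, who approves admission with one Grade 1 value, and the research monitor, whose agreement is needed for two or more, both sit on the PSRT.
- *That Protocol 8.1 and 8.10 conflict over halting.* The lowest laboratory trigger is "Two or more grade 2 laboratory abnormalities", judged at least possibly related. Because entry above Grade 1 is excluded, any Grade 2 value in an eligible subject is already a worsening. Absolute grade and worsening give the same count.
- *That small changes at a grade boundary show the fault.* Neutrophils going from 1,225 to 1,224 do move from Grade 1 to Grade 2, but that is a rise in grade and would be counted with or without a baseline grade.

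**Conclusion.** The point holds in a narrow form. The Mild count in the All values rows of Table 32 combines Grade 1 values present at entry with those that arose after vaccination, and no planned group summary separates them. Each such subject is worth 6.3 points of one test's Mild rate in a group of 16. The total cannot be estimated from the documents: the 5–30% range above is an assumption, covers any test, and in the main table supposes that every value persists.

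The primary laboratory AE endpoint, the related and not-related rows, the Grade 2 and higher counts, and the halting rules are not affected. That rests on the eligibility ceiling being observed and on AEs being recorded as SAP 3.3.1 defines them. This is a worthwhile low-cost improvement to a descriptive safety display, not a flaw in the primary endpoint or in the escalation rules.

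**What to change.** - **SAP 8.6 and Table 32:** show post-dose grade against baseline grade by test and treatment group, using the baseline rule already under Table 31 (the pre-vaccination 1 value, or screening if that is missing). Identify a value as a post-vaccination abnormality only when its grade is higher than at baseline. The cross-tabulation keeps the absolute grades visible.
- **Hemoglobin:** grade both time points on the row used for toxicity, not the row reserved for screening, so that the shift is measured on one scale.
- **SAP 6.6 item 4:** state that the same count applies, so that the PSRT summary matches the laboratory AE endpoint in SAP 3.2.1.
- **Unchanged:** eligibility in Protocol 8.1 and the halting rules in Protocol 8.10.

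The cost is programming and at most one more table. No new data are needed, because Screening and Day -7 values and severity are already planned for Listings 11 and 12.

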8.2. Randomization

Within each cohort, 20 subjects will be randomly assigned to one of 2 different treatment groups using block sizes of 5. The first cohort will be enrolled in a staggered manner in order to evaluate the safety and tolerability of the vaccine in a limited number of subjects before exposing a larger number of subjects to the study product.

The pilot group will assign subjects to each treatment group with a ratio of 4:1, so that 4 subjects will receive Invaplex_{AR}-DETOX and 1 subject will receive placebo.

After review of the safety data through Day 7 of this pilot group, if no safety concerns are identified, the remaining 15 subjects will be randomly assigned to one of the two treatment

groups in the same ratio (4:1) with 12 subjects receiving Invaplex_{AR}-DETOX and 3 subjects receiving placebo.

Subsequent dose-escalating cohorts will be randomized after review of safety data including 7 days after the final vaccination of the previous cohort. Depending on the safety profile, the PSRT will make a recommendation to the sponsor and investigator to proceed or not with the vaccination of the next cohort at a higher dose level.

Participant randomization will be generated from the Advantage eClinical system based on the enrollment sequence in the treatment table, therefore the randomization plan will also provide the maximum number of sequence numbers by site. An Emmes statistician will write code using SAS and the seed(s) for the random number generator will be documented. When a participant is randomized in Advantage eClinical only the cohort, coded treatment assignment and the sequence number will display. A second Emmes statistician will conduct and document quality control (QC) of the randomization plan, treatment table and all other related documents using the statistical considerations in the protocol. Once the treatment table has been finalized, the Emmes Systems Programmer will transfer the treatment table into the Advantage eClinical environment and the Emmes Project Manager will approve the treatment table. The person performing vaccine formulation will be provided a list of the coded treatment numbers with their corresponding unblinded treatment assignments, as well as the sealed back-up manual randomization list.

8.3. Blinding

The study is designed to keep subjects and investigators blinded until completion of the clinical phase of the trial and monitoring of the clinical data. Members of the study staff not involved in clinical outcome assessment will perform formulation of the test articles. During the course of the study, all efforts will be made to keep subjects and investigators unaware of subject assignment.

